1.0 PROTOCOL SYNOPSIS

Protocol #:	SB-STR01
Title:	A Phase 1/2A Study of the Safety and Efficacy of Modified Stromal Cells (SB623) in Patients with Stable Ischemic Stroke
Study Objectives:	Primary : To evaluate the safety and tolerability of intracranial administration of SB623 cells. Safety will be determined during 2 years post-implant.
	Secondary: To evaluate clinical and radiographic response to 3 dose levels of intracranial administration of SB623 cells. The major efficacy endpoints will be determined at 6 months; measures will also be at 1, 2, 3, 4, 9, 12, and 24 months.
Background and Rationale	SB623 cells are adult bone-marrow-derived cells that have been transiently transfected with a plasmid construct encoding the intracellular domain of human Notch-1. SB623 cells secrete factors that protect neurons in models of ischemic insult. In a rat occlusion model of stroke to the middle cerebral artery region, implantation of SB623 into and around the area of the infarct resulted in improvement of neurological behavior.
	The safety of implanted SB623 cells was evaluated in a 6-month primate study and in 2 nude rat studies (4 mos. and 12 mos.). The primates were immunosuppressed with cyclosporine and the nude rats further immunosuppressed with an anti-NK cell antibody. There were no SB623-related clinical, laboratory, or histological abnormalities found.
	The stereotactic surgical delivery of cells to patients with stroke has been shown to have an acceptable safety profile in two prior clinical studies with another product. In addition, a retrospective study of over 2,650 patients undergoing stereotactic surgery during a 28-year period at one major clinic has shown a high degree of safety with the procedure.
	Finally, the European Stroke Scale (ESS), the Modified Rankin Score, the National Institute of Health Stroke Scale (NIHSS), the Fugl-Meyer scale for motor function, and a neurocognitive battery (e.g. , Rey Complex Figure Test), have been used and validated, at least for acute stroke. Fluorodeoxyglucose positron emission tomography (FDG-PET) imaging has shown that changes in metabolic activity relative to baseline in the infarct area and surrounding areas correlated with performance on the motor subscale of the ESS.

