9.2 Duration of Patient Participation

Two years (except if there is an unresolved Grade 2 adverse event at least possibly related to the therapy, in which case the patient will be followed until resolved or reduced to Grade 1).

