10.0 STUDY ASSESSMENTS

10.1 Schedule of Study Activities

Table 4 below lists the procedures to be followed throughout the course of the study.

Confidential and Proprietary

	Scr. 1	Scr. 2	Baseline ¹	Enroll ²	Cell Admin	Follow-Up Period						Last Eval.	
Study Day			-2 to-1	-1 to 1	1	2	8						
Study Week	-3	-1	1	1	1	1	2						
Study Month								End of 1 and 2	End of 3 and 4	End of 6	End of 9	End of 12	End of 24
Informed Consent	X ³												
Demographics	Х												
Inclusion/Exclusion	Х		Х										
Medical History	Х	X^4	X ⁵	X^6									
Medication History	Х	X^4	X ⁵	X^6									
Signs & Symptoms	Х	X^4	X ⁵	X^6									
Pregnancy Test ⁷	X ⁸		X										
Physical Exam.	Х		Х									Х	Х
Vital Signs	Х	Х	Х				Х	Х	Х	Х	Х	Х	Х
Chest X-Ray and ECG	Х												
Hematology (Section 15.3)	Х	Х	Х				Х	Х	Х	Х	Х	Х	Х
Serum Chemistry (Sect. 15.3)	Х	Х	Х				Х	Х	Х	Х	Х	Х	Х
INR	Х		Х										
Occult Malig. (Sect. 10.2.2)	Х												
Lipid Panel (Section 15.3)			Х				Х	Х	Х	Х	Х	Х	Х
Cytokines (Section 15.3)			Х				Х	X (mo. 2)	X (mo. 4)	Х	Х	Х	Х
Blood for HLA antibodies	X ⁹												
Head CT					Х								
ImagingHead FDG-PET			Х							Х		Х	Х
ImagingHead MRI	X ¹⁰		Х		X ¹¹	Х	Х	X	Х	Х	Х	Х	Х

Table 4 **Study Procedures Flow Chart**

- ⁶ Only changes since Baseline
- ⁷ Only for women of childbearing potential ⁸ Serum β-HCG at Screening; serum or urine β-HCG at Baseline

¹ Only after documentation of stable stroke by two evaluations within 3 weeks prior to study entry using the NIH Stroke Scale (no more than ± 1 point)

² Enrollment only after all inclusion and exclusion criteria are verified and the patient qualifies for the study

³ Prior to any study-related procedures

⁴ Only changes since Screen 1

⁵ Only changes since Screen 2

⁹ May also be done at a pre-Screen visit

¹⁰ May instead be done at a pre-Screen visit ¹¹ Or CT overlaid with MRI from Baseline

	Scr. 1	Scr. 2	Baseline ¹	Enroll ²	Cell Admin	Follow-Up Period							Last Eval.
Study Day			-2 to-1	-1 to 1	1	2	8						
Study Week	-3	-1	1	1	1	1	2						
Study Month								End of 1	End of 3	End	End	End	End
Study Month								and 2	and 4	of 6	of 9	of 12	of 24
Clinical Stroke Evaluations	X ¹²	X ¹²	Х					X	Х	Х	Х	Х	Х
Cognitive Questionnaire			Х							Х		Х	Х
Blood for antibodies to			Х				X	\mathbf{V} (max 2)	\mathbf{V} (ma \mathbf{A})	Х	Х	X	X
SB623 and for PBMCs			Л				Λ	X (mo. 2)	X (mo. 4)	Λ	Λ	Λ	Λ
Serum Antibod. (see Sect.													
15.6 for assay schedule)													
PBMC Function (see Sect.													

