10.9 Follow-Up Period (Months 9, 12 ±7 Days)

- Physical Exam. (Month 12 only)
- Vital Signs (Including Weight for Mo. 12 only)
- Hematology (Section 15.3)
- Serum Chemistry (Section 15.3)
- Lipid Panel
- Plasma Cytokines (Section 15.3)
- Imaging--Head MRI
- Imaging—FDG PET (mo. 12 only)

- Clinical Stroke Evaluations
- Cognitive Questionnaire (Month 12 only) (Section 23.0, Table 7)
- Blood for antibodies to SB623 and peripheral blood mononuclear cells (PBMC) function assays and for storage of PBMCs (Month 12 only)
- Luminex assay for antibodies to SB623 and PBMC function assay
- Adverse Events
- Concomitant Medications (see Section 12.0)

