16.2 Adverse Event Reporting Period

The adverse event reporting period for this trial begins upon receiving the first dose of Study Drug and ends 24 weeks after the administration of SB623.

All AEs (both serious and non-serious) must be followed until resolution or until a stable clinical endpoint is reached. All measures required for AE management and the ultimate outcome of the AE must be recorded in the source document and reported to the Sponsor.

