18.4 Analysis of Safety

Adverse events, clinical laboratory data, and vital signs will be analyzed to evaluate the safety of SB623 for all patients in the Safety population through 2 years after the dose of Study Drug.

A treatment-emergent adverse event will be defined as any event not present prior to the initiation of treatment or any event already present that worsens in either intensity or frequency following exposure to study treatment.

All adverse event data will be listed per patient including severity, relationship to Study Drug, and action taken. Frequency within each treatment group of each type of adverse event will be summarized using an acceptable coding dictionary.

Laboratory data and vital signs will be listed by patient. Laboratory data values above and below normal ranges which are considered clinically significant will be indicated on the listing. Descriptive statistics will be displayed for each laboratory parameter and vital sign assessment at each time point. The mean change from baseline in each of these continuous variables will also be described.

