7.4 SAFETY ANALYSES FOR EACH COHORT AND COMBINED COHORTS

Incidence of adverse events, dose-limiting toxicities, serious adverse events, clinically significant changes in laboratory data, physical exam, and vital signs, changes in head MRI exams, antibody development, and changes in PBMC function will be analyzed to evaluate the safety of SB623 for all patients in the safety population through 2 years post study treatment administration.

Physical exam and vital sign data, absolute and change from baseline, will be listed by patient by visit. Laboratory data values falling above or below normal range and considered clinically significant will be indicated on the corresponding laboratory listings. Any changes in MRI images at visits post study treatment administration will be indicated in the MRI listing. Presence of antibodies to SB623 (see Section 7.4.6) will be indicated in the antibody listing by patient by visit. PBMC function, the cytokine measurements, will be listed by patient by visit. Descriptive statistics for absolute and change from baseline values will be displayed for each continuous laboratory parameter at each time point.

This Document is Company Confidential Page 15 of 28

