7.4.1 Adverse Events

A treatment-emergent adverse event (TEAE) is defined as any event not present prior to study treatment administration or any event already present that worsens in either intensity or frequency following exposure to study treatment.

Adverse events will be classified based on the Medical Dictionary for Regulatory Activities (MedDRA) dictionary, version 15.1 (or higher). Analyses will be conducted on preferred term and primary system organ class (SOC). All adverse event data will be listed per patient including severity, relationship to study treatment, and action taken. Event severity is based on the World Health Organization (WHO) standard toxicity criteria (STC).

A Dose-limiting toxicity (DLT) will be defined as any grade 3 or 4 event which is at least possibly related to study product or administration procedure.

The adverse event reporting period for this trial begins upon receiving the dose of study treatment and ends 24 months after the administration of SB623.

The following summaries of AEs will be provided:

- TEAEs by MedDRA SOC and by preferred term
- TEAEs by maximum severity (mild, moderate, severe, life-threatening) by MedDRA SOC and preferred term
- TEAEs by relationship to study treatment by not related (includes unrelated and unlikely related) or related (includes possibly, probably, and definitely related) by MedDRA SOC and preferred term.
- AEs resulting in discontinuation from the study, by MedDRA SOC and preferred term
- SAEs by MedDRA SOC and preferred term
- The following listings of adverse events will be provided (TEAEs will be denoted in each listing):
 - o All AEs
 - All Dose-Limiting Toxicities (DLTs)
 - o Adverse events resulting in discontinuation from the study
 - o Deaths (if any)
 - o Serious adverse events
 - AE mappings to MedDRA dictionary terms

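### Protocol 16.2 closes adverse event reporting at 24 weeks, although the protocol sets, schedules and analyses safety over 2 years and the SAP says 24 months

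*Protocol*

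**What the plan says.** Protocol 16.2 says the AE reporting period "begins upon receiving the first dose of Study Drug and ends 24 weeks after the administration of SB623". It adds that AEs are followed until they resolve or stabilise.

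The rest of the protocol works to 2 years:
- The primary objective in the synopsis: "Safety will be determined during 2 years post-implant".
- Participation in 9.2: "Two years (except if there is an unresolved Grade 2 adverse event at least possibly related to the therapy", in which case follow-up is extended.
- Section 18.4 analyses AEs, laboratory data and vital signs "through 2 years after the dose of Study Drug".
- Table 4 and sections 10.9 and 10.10 list Adverse Events as an assessment at Months 9, 12 and 24.

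In the SAP, section 7.4.1 says the period "begins upon receiving the dose of study treatment and ends 24 months after the administration of SB623". Section 7.4 analyses AEs, dose-limiting toxicities (DLTs) and serious adverse events (SAEs) "for all patients in the safety population through 2 years post study treatment administration".

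**The concern.** The primary objective is safety over 2 years, and AEs, DLTs and SAEs are among the endpoints listed for it in SAP 6.2. A site that applies 16.2 as written has no reason to enter an event that begins after week 24. A site that works from Table 4 will enter it. Both would be following the protocol.

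If sites differ, Tables 14.3.1.1 to 14.3.1.5 and the AE, DLT and SAE listings mix two collection periods. An empty entry after week 24 then cannot be read as no event, because it may mean that nothing was collected. With 18 patients at up to 8 sites and no control group, a handful of late events can change the safety picture.

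The problem is confined to event data. Laboratory tests, vital signs, antibodies, peripheral blood mononuclear cell function and cytokines have their own schedule to Month 24. MRI is partly exposed: SAP 7.4.2 keeps a flag for presence or absence of change at each follow-up visit, but the details of a change are reported as an AE.

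**Working it through.** The 24 weeks is a stipulated duration with no calculation behind it, so there is no figure to reproduce. The check compares it with the other durations and the visit schedule.

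**Inputs**
- Reporting period: 24 weeks (Protocol 16.2).
- Safety follow-up: 2 years (Protocol synopsis, 9.2 and 18.4).
- AE assessments: Days 1, 2 and 8, and Months 1, 2, 3, 4, 6, 9, 12 and 24, which makes 11 (Table 4).
- Visit windows: ±7 days at Months 6, 9 and 12; ±14 days at Month 24 (10.8 to 10.10).
- Sample size: 18 evaluable patients (synopsis).
- Month length is not defined. I take 28 days and 30.44 days (365.25/12) as the range.

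**Share of follow-up covered**
- 24 × 7 = 168 days; 2 × 365.25 = 730.5 days.
- 168/730.5 = 0.230, so 23% is covered.
- 730.5 − 168 = 562.5 days, or 77%, is not covered.

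**Scheduled AE assessments after day 168**

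| | 28-day months | 30.44-day months |
|---|---|---|
| Month 6 (nominal day) | 168 | 182.6 |
| Month 6 window | 161 to 175 | 175.6 to 189.6 |
| Earliest Month 9 visit | 252 − 7 = 245 | 273.9 − 7 = 266.9 |
| Gap from day 168 to that visit | 77 days | 98.9 days |
| Assessments nominally after day 168 | Months 9, 12, 24: 3/11 = 27% | Months 6, 9, 12, 24: 4/11 = 36% |

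Months 9, 12 and 24 fall outside the period under either convention. Month 6 depends on the convention, and it is also the first visit after Month 4 at which events arising up to week 24 can be collected. The conclusion therefore does not use it.

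**Patient time**
- Total with full follow-up: 18 × 730.5/365.25 = 36.0 patient-years.
- After week 24: 18 × 562.5/365.25 = 27.7 patient-years.

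**Could the passages be read together?** The instruction to follow AEs to resolution (16.2 and 16.6) concerns events that have already begun, not new onsets. No text restricts collection after week 24 to a subset such as related or serious events. Nothing ranks Table 4 above 16.2 or the reverse. I found no reading that satisfies 16.2, 18.4 and Table 4 together.

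**The case against.** The strongest reply is that one sentence stands against many. Table 4 carries AE assessment to Month 24, 16.1 asks for alertness to AEs throughout the study, 16.3 requires all AEs on the CRF with no cut-off, and the SAP analyses 24 months. Section 16.2 is headed as a reporting period and 16.3 as recording, so a site could reasonably keep recording. On this view 16.2 is probably a slip of weeks for months, and little or nothing was lost.

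Most of this is fair. The near-identical wording in SAP 7.4.1 does suggest a slip, though the documents do not confirm it, and a loss of zero is possible. But the distinction between reporting and recording is not reliable, because SAP 7.4.1 uses the same term for the period behind its AE tables. The weight of the other passages shows that sites had conflicting instructions. It does not show which one they followed.

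Two limits stand. First, the upper bound applies to the CRF-based AE tables: reaching it requires every site to disregard the AE row of Table 4 at Months 9, 12 and 24, and some late events could still surface through expedited or ethics committee reporting. Second, the SAP rests on protocol amendment 4.5 and the protocol reviewed is amendment 5.0, so a mismatch between the two documents could be a version effect. The conflict inside the protocol does not depend on the SAP.

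**Conclusion.** The concern holds, and the passages must be reconciled. The rule in 16.2 is incompatible with the 2-year primary safety objective, the 2-year AE analysis and the visit schedule of the same protocol. It is an internal inconsistency, since no passage presents 24 weeks as a deliberate choice.

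Taken literally, 16.2 leaves 77% of follow-up, 27.7 of 36.0 patient-years, and at least 3 of the 11 scheduled AE assessments outside the reporting period. The patient-time figures assume 18 patients with full 2-year follow-up. The count of 3 assessments assumes 28-day months; with calendar months it is 4.

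The loss from the AE tables lies between none and every AE with onset after week 24. Events that began earlier are still followed. Because the contradiction bears on the primary objective and costs little to remove, it should be corrected.

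**What to change.** Amend Protocol 16.2 so that the AE reporting period ends 24 months after administration, or at the Last Evaluation visit. That agrees with the synopsis, 18.4, Table 4 and SAP 7.4.1. It is one wording change and adds no visits or procedures, because Table 4 already lists AE assessment through Month 24.

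The SAP addendum of December 2016 describes analyses as performed and refers to final data, so collection may be complete. In that case the amendment comes too late to help, and the effective remedy is to establish from each site which period it applied, state this in a footnote to Tables 14.3.1.1 to 14.3.1.5 and the related listings, and identify any site that stopped at week 24. The cost is a query to up to 8 sites and the footnote.

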16.3 Recording of AEs

All AEs, regardless of severity, seriousness, or presumed relationship to Study Drug, must be recorded using medical terminology in the source document and on the CRF. Events will be recorded at all study sites using standard terminology provided by the Sponsor or designate (*e.g.*, CRO), such as COSTART terminology.

The WHO (World Health Organization) Standard Toxicity Criteria (STC) will be used to assist in categorizing and grading adverse events. A copy of the WHO STC will be provided in the study documents. Whenever possible, a diagnosis should be given when signs and symptoms are due to common etiology (*e.g.*, cough, runny nose, sneezing, sore throat, and head congestion should be reported as "upper respiratory infection").

16.4 Assessing Relationship of AE to Study Drug

The Investigator must record his/her opinion concerning the relationship of the AE to study therapy on the Adverse Event CRF. Table 5 below provides guidance for assigning relationship to Study Drug.

Table 5Relationship of Adverse Event to the Administration of the Study Drug

Unrelated	There is not a temporal relationship to study drug administration (e.g., too early,
	too late, or study drug not taken), or there is a reasonable causal relationship
	between another drug, concurrent disease, or circumstance and the AE.
Unlikely	There is a temporal relationship to study drug administration, but there is not a
	reasonable causal relationship between the study drug and the AE (i.e., the AE
	is doubtfully related to study drug)
Possibly	There is a reasonable causal relationship between the study drug and the AE.
	Information related to withdrawal of study drug is lacking or unclear
Probably	There is a reasonable causal relationship between the study drug and the AE.
	The event responds to withdrawal of study drug. Re-challenge is not required
Definitely	There is a reasonable causal relationship between the study drug and the AE.
	The event responds to withdrawal of study drug, and recurs with re-challenge,
	when clinically feasible

16.5 Reporting Serious or Unexpected AEs

Any Serious Adverse Event, including death that occurs during this study (from the first dose of Study Drug up to and including 4 weeks following the last dose of Study Drug), whether or not the event is considered to be related to the study treatment, must be reported immediately (within 24 hours after the site becomes aware of the event) to the Principal Monitor.

The contact information for reporting SAEs is as follows:

[name]. [contact] ext 44 [contact] Email: [contact] The Investigator is encouraged to discuss with the Principal Monitor any adverse experiences for which the issue of reportability is unclear or questioned.

A verbal or faxed Serious Adverse Event Report must be followed by a written report signed by the Investigator within 48 hours. Written notification must include SAE start and stop dates, Study Drug dosage and treatment history, description of SAE with applicable laboratory test results, list of concomitant medications, relationship of Study Drug to SAE, autopsy report (if applicable), and any other relevant information such as medical history, hospital discharge summary, *etc.* The report should be as complete as possible without delaying Sponsor notification.

An SAE Report should be prepared containing as much available information concerning the event as possible so that a written report can be filed with the appropriate regulatory authorities. Any SAE follow-up information requested by the Sponsor or the Sponsor's designee should be provided in a timely manner.

Upon receipt of notification of any Serious Adverse Event, the Sponsor will immediately conduct an evaluation of the event and take action indicated by the results of the evaluation. This may include notification of the FDA, other Investigators, IRBs and/or the suspension or termination of the study. The Investigator is required to report Serious Adverse Events and Unexpected Adverse Events to the local Ethics Committee (EC) or Institutional Review Board (IRB) in accordance with the EC/IRB bylaws.

All additional follow-up evaluations of the SAE must be reported to the Sponsor. These data should be faxed to the Principal Monitor at [contact] as soon as they are available.

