Study Design	This is an open-label safety study of stereotactic, intracranial injection of SB623 cells in patients with hemiparesis from stable ischemic stroke who have remained stable during the prior 3 weeks (based on NIHSS assessments at weeks -3 and -1). While primarily a safety study, efficacy parameters will also be evaluated. Three cohorts will receive escalating single doses of SB623, which are to be stereotactically implanted into grey or white matter sites adjacent to the infarct region. One burr-hole craniostomy will be created, and cells implanted using 3 needle tracks with 5 deposits for each track at varying depths around the damaged area. Cell

	implantation will be standardized as to volume (20 μ L/denosit) and rate (10
	implantation will be standardized as to volume ($20 \mu L/deposit$) and rate ($10 \mu L/min$), with spacing between each implant of approximately 5-6 mm. Each deposit is expected to take approximately 2-3 minutes, with each needle track being completed within 15 minutes. Each cohort will consist of 6 subjects defined by an increasing total number of cells implanted. Safety will be monitored by the Investigator, Principal Monitor, Medical Monitor, and an external Data Safety Monitoring Board. For the first cohort, a single patient will first be dosed, then evaluated over a 2 week period for safety prior to dosing the next member of the cohort. This 2- week interval will continue between each of the remaining members of this cohort. If the safety profile is acceptable for a cohort, and after review by the DSMB, the first patient in each subsequent cohort will be dosed, beginning 4 weeks after dosing of the last patient of the prior cohort. For the second and third patients in each of the subsequent cohorts, there will be an interval of 2 weeks after the prior patients prior to further enrollment.
	Safety will be monitored by clinical symptoms, laboratory findings, and MRI brain imaging. Two or more serious adverse events will trigger a review by the DSMB before continuing enrollment. Possible efficacy will be determined based on changes in the clinical measures of stroke through standardized assessments and on FDG-PET brain imaging.

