9.0 INVESTIGATIONAL PLAN

9.1 Overall Study Design

This is an open-label study of stereotactic, intracranial injection of SB623 cells (SB623 cells) in patients with hemiparesis from stable ischemic stroke who have remained stable during the

prior 3 weeks (as documented by NIHSS assessments at weeks -3 and -1). Three cohorts will receive escalating singe doses of SB623, which are to be stereotactically implanted into grey or white matter sites adjacent to the infarct region. One burr-hole craniostomy will be created, and cells implanted using 3 needle tracks with 5 cell deposits for each track at varying depths. Cell implantation will be standardized as to volume (20 uL/deposit) and rate $(10 \,\mu L/min)$, with spacing between each implant of approximately 5-6 mm. Each deposit is expected to take approximately 2-3 minutes, with each needle track being completed within 15 minutes. Each cohort will consist of 6 subjects defined by an increasing total number of cells implanted. Safety will be monitored by the Investigator, Principal Monitor, Medical Monitor, and an external Data Safety Monitoring Board (DSMB). For the first cohort, a single patient will first be dosed, then evaluated over a 2 week period for safety prior to dosing the next member of this cohort. This 2-week interval will continue between each of the remaining members of the cohort. If the safety profile is acceptable for a cohort, and after review by the DSMB, the first patient in each subsequent, sequential cohort will be dosed, beginning 4 weeks after dosing of the last patient of the prior cohort. For the second and third patients in each of the subsequent cohorts, there will be an interval of 2 weeks after the prior patients prior to further enrollment.

Safety will be monitored by clinical symptoms, laboratory findings, and MRI brain imaging. Efficacy will be determined based on changes in the clinical measures of stroke and on FDG-PET brain imaging.

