14.0 STOPPING RULES

A dose-limiting toxicity will be defined as any grade 3 or 4 events which are at least possibly related to study product or administration procedure. If the first patient in a cohort has a dose-limiting toxicity attributable to the SB623 cells, then no further patients will be dosed in that cohort until a comprehensive evaluation has been conducted. If 2 of 6 patients in a cohort have a dose-limiting toxicity attributable to the SB623 cells, then no further patients will be dosed in that or higher-dose cohorts. Each dose-limiting-toxicity will be evaluated by the DSMB.

In addition, adverse events attributable to the surgical procedure, such as intracranial infection, intracranial bleeding, or seizures, shall be subject to review by the DSMB

The DSMB shall be the final arbitrator for attributions.

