An **Unexpected Adverse Event** is any AE that is not identified in nature, severity, or frequency in the current Investigator's Drug Brochure or product information. For this study, an unexpected adverse event also includes neurological deterioration, procedural complications, seizures, benign and malignant tumors and pregnancy, and will be submitted as expedited reports.

An Unexpected Adverse Drug Reaction (ADR) is an adverse reaction, the nature or severity of which is not consistent with the applicable product information (*e.g.*, Investigator's Brochure for an unapproved investigational medicinal product). All noxious and unintended responses to a medicinal product related to any dose should be considered ADRs. All serious and unexpected ADRs will have expedited reporting to the FDA.

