17.0 EXTERNAL DATA SAFETY MONITORING BOARD

An External Data Safety Monitoring Board (DSMB) will continuously evaluate toxicity and mortality rates, and recommend appropriate actions, according to the DSMB Charter.

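### The 24-hour SAE notification duty ends 4 weeks after the single implant, but the two-SAE enrolment hold has no time limit and must work throughout dose escalation

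*Protocol*

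**What the plan says.** Protocol 16.5 obliges the site to tell the Principal Monitor of any SAE, related or not, within 24 hours of learning of it. The obligation runs "from the first dose of Study Drug up to and including 4 weeks following the last dose of Study Drug". The synopsis states "Three cohorts will receive escalating single doses of SB623", so first and last dose are the same event and the duty lasts 4 weeks from implantation.

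The synopsis also states "Two or more serious adverse events will trigger a review by the DSMB before continuing enrollment", and SAP 7.6 repeats this. Neither gives a period over which SAEs count, and Section 14.0 (Stopping Rules) does not mention this trigger. The dosing stop in 14.0 ("If 2 of 6 patients in a cohort have a dose-limiting toxicity attributable to the SB623 cells") has no period either.

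The documents use other safety horizons elsewhere. Protocol 16.2 ends the AE reporting period at 24 weeks and SAP 7.4.1 ends it at 24 months. The synopsis and Protocol 18.4 assess safety over 2 years, and Table 4 collects AEs up to Month 24.

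Some routes are not tied to 4 weeks. Section 16.1 lists seizures, procedural complications and neurological deterioration, and the list ends "benign and malignant tumors and pregnancy, and will be submitted as expedited reports". Section 14.0 sends surgical events such as bleeding, infection and seizures to the DSMB. Section 17.0 says the DSMB "will continuously evaluate toxicity and mortality rates".

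**The concern.** The two-SAE hold is prospective: the DSMB must review before the next patient is enrolled. That works only if an SAE becomes known faster than patients are dosed, and in cohort 1 a patient is dosed every 2 weeks. The 24-hour duty meets that need, but for each patient it lapses after 4 weeks, while the hold carries on.

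Safety is the primary objective, Protocol 3.8 reports no earlier clinical study of SB623, and the total dose doubles from each cohort to the next (2.5, 5.0 and 10 million cells). If a second SAE occurs after week 4 in its patient, a further implant could take place before the sponsor and DSMB know that the hold should apply.

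**Working it through.** **The plan's own figure.** Protocol 18.5 gives a chance below 5% of seeing no dose-limiting toxicity (DLT) in 6 patients if the true rate is 40%. This reproduces: (1 − 0.40)^6 = 0.6^6 = 0.0467. It concerns DLTs that occur, not when anyone learns of them, so it does not settle this point.

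**Inputs (Protocol 9.1).**
- "Each cohort will consist of 6 subjects".
- Cohort 1: after the first patient, "This 2-week interval will continue between each of the remaining members of the cohort".
- Each later cohort opens 4 weeks after the last dose in the cohort before, following DSMB review.
- Cohorts 2 and 3: a 2-week interval is stated for patients 2 and 3 only, so the spacing of patients 4 to 6 is an assumption. Three readings are shown.
- Window from 16.5: 4 weeks per patient.

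**Method.** For a patient dosed at week d and seen from calendar week T, follow-up is T − d. The part inside the window is the smaller of 4 and T − d.

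**Cohort 1 when cohort 2 can open.** Doses fall at weeks 0, 2, 4, 6, 8 and 10, so cohort 2 can open at 10 + 4 = week 14.
- Follow-up: 14 + 12 + 10 + 8 + 6 + 4 = 54 patient-weeks.
- Inside: 6 × 4 = 24.
- Outside: 54 − 24 = 30, and 30/54 = 56%.

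From week 14 onwards all six cohort 1 patients have reached or passed the end of their window. A slower schedule adds follow-up but no time inside the window, so the share outside would rise.

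**All 18 patients up to the last dose in the trial.**

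| Patients 4–6 of cohorts 2 and 3 | Last dose (week) | Follow-up, cohorts 1 + 2 + 3 | Inside 4 weeks | Outside |
|---|---|---|---|---|
| Dosed with patient 3 | 26 | 126 + 54 + 6 = 186 | 24 + 24 + 6 = 54 | 132 (71.0%) |
| All 2 weeks after patient 3 | 30 | 150 + 72 + 12 = 234 | 24 + 24 + 10 = 58 | 176 (75.2%) |
| Every patient 2 weeks apart | 38 | 198 + 114 + 30 = 342 | 24 + 24 + 18 = 66 | 276 (80.7%) |

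**Effect of a longer window.** With the 24 weeks of Protocol 16.2 in place of 4, the patient-weeks outside fall to 2/186 (1.1%), 12/234 (5.1%) and 54/342 (15.8%). With 24 months, none of the escalation is outside.

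**Timing of the fallback.** Suppose patient 1 has an SAE at week 5 that would be the second in the trial. The next scheduled visit is the end of Month 2: 2 × 365.25/12 = 60.9 days, or week 8.7, with a window of ± 5 days. On the shortest schedule patients 4 and 5 are dosed at weeks 6 and 8. Scheduled AE capture alone therefore need not deliver the event before those implants.

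**The case against.** The strongest reply is that SAEs after week 4 have other routes.
- Section 16.1 calls for expedited reports of its listed events.
- Section 14.0 puts surgical events before the DSMB.
- Sections 16.2 and 16.6 require AE management and outcome to be reported to the sponsor.
- Sections 16.5 and 19.2 require SAEs to go to the ethics committee, with timely copies of the correspondence to the sponsor.
- Section 19.8 provides frequent telephone contact and site visits.
- Under SAP 7.6 the DSMB reviews all patients in a cohort before the next one opens, and its charter, which is not among the documents, may add more.

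Much of this stands. A reader might infer that a late seizure or intracranial bleed would go unreported, or that cohorts would be escalated without the DSMB seeing late SAEs. The documents do not support that: such events fall, or may fall, under 16.1 or 14.0, and the cohort review is not limited to events notified within 24 hours. What remains is narrower. None of these routes states a site-to-sponsor deadline for an SAE, and 16.1 does not cover every SAE, whereas the hold counts any SAE.

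A reader might also tie the gap to the 2-of-6 DLT rule. That link is only partial. A DLT is defined by grade and relatedness, not seriousness, so a non-serious DLT has no 24-hour route under 16.5 even in the first week.

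Finally, the last dose in 16.5 could be read as the last dose in the whole trial, which would cover the escalation. The text does not say so, and the per-patient reading is the natural one. If the wider reading was meant, a clarifying sentence is still needed.

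**Conclusion.** The gap is real and limited. The only SAE route from site to sponsor with a fixed deadline closes 4 weeks after each implant, while the two-SAE hold stays open without limit. On the shortest schedule 56% of cohort 1 follow-up is outside the window when cohort 2 can open, and 71% to 81% of all follow-up is outside by the last dose. The consequence is possible delay: an SAE after week 4 may not reach the sponsor and DSMB before the next implant.

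These percentages must not be read as the share of SAEs missed. They measure exposure time, and the documents give no event rates by time since implantation. The 14-week minimum is specific to cohort 1. Cohort 2 can clear in 8 to 10 weeks under the two tighter readings, with 6/30 (20%) to 12/36 (33%) of its own follow-up outside. The result rests on the per-patient reading of 16.5, on minimum dosing intervals, and on the charter not setting a site deadline of its own.

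**What to change.** - In Protocol 16.5, replace the 4-week limit so that 24-hour SAE notification runs for the full AE reporting period.
- Reconcile that period. Protocol 16.2 says 24 weeks and SAP 7.4.1 says 24 months, while the synopsis and Protocol 18.4 assess safety over 2 years. One period should be stated and used in all four places.
- Reconcile Section 14.0 with the two-SAE hold in the synopsis and SAP 7.6. The sponsor and DSMB should state the period over which SAEs and DLTs count; no counting rule is proposed here.

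The cost is a few sentences and a few more expedited SAE reports from 18 patients. No visit or procedure is added, because AE collection is already scheduled up to Month 24.
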